8.3 Randomization Code Creation and Storage

Randomization personnel of the sponsor or designee will generate the randomization schedule and will provide it to the site pharmacist prior to the start of this study. A revised randomization schedule for Cohorts 13 to 15 will be provided to the site pharmacist. All randomization information will be stored in a secured area, accessible only by authorized personnel.

8.4 Investigational Drug Blind Maintenance

The investigational drug blind is maintained through a randomization schedule held by the dispensing pharmacist. The site-designated study personnel will maintain the investigational drug blind information.

8.5 Unblinding Procedure

The investigational drug blind shall not be broken by the investigator unless information concerning the investigational drug is necessary for the medical treatment of the subject. All study assessments and causality should be performed, if possible, prior to unblinding. In the event of a medical emergency, if possible, the medical monitor should be contacted before the investigational drug blind is broken to discuss the need for unblinding.

The sponsor must be notified as soon as possible if the investigational drug blind is broken. The date, time, and reason the blind is broken must be recorded in the source documents, and the same information (except the time) must be recorded on the eCRF.

If any site personnel are unblinded, investigational drug must be stopped immediately and the subject withdrawn from the study.

No change should be made to any assessment of the subject after unblinding.

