7.6 Procedures for Discontinuation or Withdrawal of a Subject

The investigator may discontinue a subject's study participation at any time during the study when the subject meets the study termination criteria described in Section 7.5. In addition, a subject may discontinue his or her participation without giving a reason at any time during the study. Should a subject's participation be discontinued, the primary criterion for termination must be recorded by the investigator. In addition, efforts should be made to perform all procedures scheduled for the Early Termination Visit.

Enrolled participants who withdraw from the study for reasons other than safety may be replaced to ensure adequate numbers of evaluable subjects. The decision to replace a withdrawn subject will be made at the discretion of Takeda and the investigator.

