8.1.3 Dose and Regimen

The investigator or investigator's designee will instruct the subject on dosing procedures. All dosing will occur while subjects are in the clinic under the supervision of the principal investigator

or designee (except Days -18 to -11 during Cohorts 10 to 12 where the subject will self-administer donepezil and Days 3 to 10, 12 to 19, 43 to 50, and 52 to 59 during Cohort 16 where the subject will self-administer TAK-071 or placebo each morning at home). The doses taken in the clinic will be administered to the subjects by the investigator or investigator's designee. The exact time of dose will be recorded in the source documents and on the appropriate eCRF.

The planned initial dose of TAK-071 or matching placebo for Cohort 1 is 1 mg. TAK-071 is dosed on the morning of Day 1 after fasting for at least 8 hours. Cohorts 2 through 6, 18, and 19 will escalate through the SRD levels and Cohorts 7 through 9 through the MRD dose levels. Additionally, Cohorts 10 to 12 will be pretreated for 3 weeks with 5 mg donepezil orally continuing through Day 21. In healthy subjects in Cohorts 10 to 12, donepezil will be administered in the morning, shortly before or after TAK-071; the precise relative timing will be confirmed once TAK-071 PK data are available. Cohorts 9 and 13 through 15 will have 1 dose of TAK-071 on Day 1 followed by a 7-day washout period before administration of 21 daily doses of TAK-071. Subjects in Cohorts 20 to 22 will be administered as a single dose of TAK-071 or placebo on Day 1, and a single dose of donepezil or placebo approximately 24 hours later on Day 2.

In Cohort 16, subjects with MCI or mild AD who are stable on donepezil will be randomized to 1 of 2 possible treatment sequences consisting of 2 periods and 2 treatments, alternating in a crossover fashion. In each period, subjects will receive 1 of the following treatments: TAK-071 QD for 21 days (Treatment A) or 21 days of matching placebo (Treatment B). Background 10 mg QD donepezil treatment will be administered in the evening just before bedtime.

In Cohort 17 (Relative BA and FE), TAK-071 DIC or tablet will be administered as a single dose (Regimen A, B, and C) in a cross-over design over 3 periods, with a 21-day washout after each treatment. The planned dose is 10 mg in each of the 3 periods. Diet assigned to each regimen is described in Section 7.4.

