8.2 Investigational Drug Assignment and Dispensing Procedures

Subjects will be assigned, in the order in which they are randomized into the study, to receive their treatment according to the randomization schedule allocated to the site. The Randomization Sequence Number will be entered onto the eCRF.

For each dosing cohort in SRD, MRD, and BA/FE parts, randomized subjects will be assigned a 5-digit randomization number in the order which they are enrolled. Randomization sequence numbers will be XYY01 to XYY08 (Cohorts 7 to 12) or XYY06 (Cohorts 13 to 15), where X refers to SRD (Part 1) or MRD (Part 2) and Y refers to cohort number.

For example:

- Subjects in SRD Cohort 1 will have randomization sequence numbers 10101 to 10108, and subjects in SRD Cohort 2 will have numbers 10201 to 10208.
- Subjects in MRD Cohort 7 will have randomization sequence numbers 20701 to 20708, and subjects in MRD Cohort 11 will have numbers 21101 to 21108.
- Subjects in MRD Cohort 13 will have randomization sequence numbers 21301 to 21306.
- Subjects in BA/FE Cohort 17 will have randomization sequence numbers 21701 to 21712.
- Subjects in Cohort 20 will have randomization sequence numbers 12001 to 12012.

If a subject needs to be replaced, the replacement subject will receive the same treatment or treatment sequence of the subject being replaced. The replacement randomization number will be 50 larger than the randomization number of the subject who is being replaced. For example, randomization number 10251 will be used for the subject who replaces the subject who had randomization number 10201, using the same treatment or treatment sequence in Cohort 2.

This 5-digit number will be used by the clinical site to facilitate the prelabeling of PK samples and will be the only subject identifier used on all PK and/or PD sample collections. It should also be contained on the PK transport vials shipped to the bioanalytical laboratory and will be used by the laboratory to report the subject data results. This 5-digit number should only be used for the purposes described in this section. It does not replace the 3-digit subject number that is assigned at the time the informed consent is obtained and used for all other procedures to identify the subjects throughout the study.

Study drugs will be dispensed in the clinic under the supervision of the investigator or designee.

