9.1.6 Vital Sign Procedure

In subjects who are not undergoing CSF collection (Cohorts 2, 4 to 8, and 10 to 22), vital signs will include body temperature (oral), respiratory rate, and orthostatic blood pressure and pulse (bpm).

In subjects who have completed enrollment for Cohort 1 at the time of this amendment and in subjects who are undergoing CSF collection (Cohorts 3 and 9), vital signs include body temperature (oral), respiratory rate, supine blood pressure (resting more than 5 minutes), and pulse (bpm).

Vital signs should be collected daily, predose and upon morning rising on days during confinement. In addition, vital signs should be collected in Cohorts 3 and 9 at approximately 5 hour postdose on Day 1 and Day 8 (Cohort 9 only). Vital signs may be repeated. All measurements will be recorded on the source documents and in the eCRF.

When vital signs are scheduled at the same time as blood draws, the blood draw will take priority, and vital signs will be obtained within 0.5 hour before the scheduled blood draw.

For BA/FE Cohort 17, for the fed regimen, if vital signs coincide with a meal, vital signs will take precedence followed by the meal.

For Cohorts 2, 4 to 8, and 10 to 22, orthostatic blood pressure and pulse will be measured at predose and at 2, 4, 6, 8, and 12 hours postdose in the first 24 hours after the initial dose of TAK-071 (Day 1) and then afterwards on days while subjects are in the phase 1 unit. Orthostatic blood pressure will be measured as follows [23]:

1. Have the patient lie down for 5 minutes.
2. Measure blood pressure and pulse rate.
3. Have the patient stand.
4. Repeat blood pressure and pulse rate measurements after standing 1 and 3 minutes.

A drop in bp of ≥ 20 mm Hg, or in diastolic bp of ≥ 10 mm Hg, or experiencing lightheadedness or dizziness is considered abnormal [23].

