C-SSRS (q)	X	X					X		X	(X)
CCI										
Pupillometry (s)		X	X	X						

Footnotes are on the following page.

ET=Early Termination Visit, HBsAg=hepatitis B surface antigen, HCV=hepatitis C virus.

- (a) A PK blood sample should be collected at the Early Termination Visit, if possible.
- (b) Follow-up will occur by telephone on Day 12 (± 2) unless abnormal clinically significant findings are observed upon discharge. In these cases, subjects must then be brought back to the clinic for re-evaluation per investigator's discretion.
- (c) Vital signs (oral temperature, respiration, pulse, and blood pressure) will be obtained as indicated. In addition, orthostatic blood pressure will be measured at predose and at 2, 4, 6, 8, and 12 hours postdose in the first 24 hours after the initial dose of TAK-071 and then daily afterwards while subjects are confined in the phase 1 unit as detailed in Section 9.1.6.
- (d) Height and BMI will be collected at Screening only.
- (e) All ongoing medications will be recorded from Screening and throughout the study.
- (f) Blood and urine samples for clinical laboratory tests (hematology, coagulation, serum chemistry, urinalysis) will be collected as indicated. On Day 1, the urine sample for urinalysis will be taken predose (within 2 hours prior to dosing) and the blood sample will be taken 1 hour postdose. On subsequent days, blood and urine samples will be taken upon rising in the morning under fasted condition.
- (g) During the course of the study, regular serum hCG pregnancy tests will be performed for female subjects and subjects will receive continued guidance with respect to the avoidance of pregnancy as part of the study procedures. In addition to a negative serum hCG pregnancy test at Screening, female subjects must have a negative serum hCG pregnancy test at Check-in prior to receiving the first dose of study drug.
- (h) FSH concentration will be obtained from postmenopausal women (defined as continuous amenorrhea of at least 2 years and not surgically sterile).
- (i) A standard 12-lead ECG will be recorded at Screening, Check-in (Day -1), Day 1 (predose [within 60 minutes prior to dosing], and at 0.5, 1, 2, 4, and 8 hours postdose), and Days 2 through 5 (upon morning rising) or ET. Single ECGs will be taken at all visits.
- (j) Blood samples for PGx analysis will be collected as follows: 6 mL for DNA on Day 1; 2 \times 2.5 mL for RNA analysis on Day 1 (predose and 12 hours postdose) and Day 5.

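### Section 8.5 withdraws an unblinded subject from the study as well as from drug; in single-dose subjects this only cuts short the remaining scheduled safety and PK collection (cheap improvement, low priority)

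*Protocol*

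**What the plan says.** Protocol 8.5 limits code breaks to one ground: the "blind shall not be broken by the investigator unless information concerning the investigational drug is necessary for the medical treatment of the subject". The section then sets the consequence: "If any site personnel are unblinded, investigational drug must be stopped immediately and the subject withdrawn from the study". It gives no option to stay under observation off drug. It does ask that assessments and causality be completed before the code is opened where possible, and it bars changes to assessments afterwards.

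Cohorts 1 to 6, 18 and 19 receive one TAK-071 dose on Day 1. Cohorts 20 to 22 receive TAK-071 or placebo on Day 1 and "a single dose of donepezil or placebo approximately 24 hours later on Day 2" (8.1.3). Scheduled observation runs on to release on Day 5, a Day 8 visit and a call on Day 12 (±2).

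Some follow-up survives withdrawal:
- a best-effort Early Termination visit (7.6), with a PK sample if possible (9.3.5);
- monitoring of existing AEs (10.2.1.2) and of verified clinically significant laboratory abnormalities (9.1.9);
- clinic re-evaluation for clinically significant findings at discharge (9.3.6);
- SAE follow-up to resolution (10.3).

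On replacement, 7.6 says: "Enrolled participants who withdraw from the study for reasons other than safety may be replaced to ensure adequate numbers of evaluable subjects". Section 8.2 adds that "the replacement subject will receive the same treatment or treatment sequence of the subject being replaced".

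**The concern.** The rule joins two separate actions, stopping drug and leaving the study. Stopping drug can protect a subject who still has doses to come. After the last dose it has no effect, and only the withdrawal operates.

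Because the permitted ground for a blind break is medical treatment, the subject affected is likely to be one with a significant event, whose later ECG, laboratory and PK course is worth having. Cohorts 20 to 22 exist to show how TAK-071 plus donepezil is tolerated, and each has only 6 combination subjects. One truncated subject is 1 of 6.

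**Working it through.** The plan gives no figure for this, so the check is a count from the schedules and a simple PK illustration.

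**Scenario.** A TAK-071+donepezil subject in Cohorts 20 to 22, blind broken 28 h after TAK-071. That is 4 h after donepezil, at the end of its reported tmax range of 3 to 4 h (6.2.2.4).

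**PK samples, Protocol Table 9.i.**
- TAK-071 has 20 postdose times. Those after 28 h are 30, 32, 36, 40, 48, 56, 64, 72, 96 and 168 h: 10 lost.
- Donepezil has 14 postdose times. Those after 4 h are 6, 8, 12, 16, 24, 32, 40, 48, 72 and 144 h: 10 lost. Of the 9 times up to 24 h, 5 are lost (6, 8, 12, 16, 24 h).

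**PK samples, SAP 7.10.1.** This schedule differs slightly. TAK-071 has 19 times with 9 after 28 h; donepezil has 16 times with 12 after 4 h. On either schedule one Early Termination sample may be recovered.

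**Safety sets, Protocol Appendix A for Cohorts 20 to 22.** ECGs are taken on "Days 2 through 5 (upon morning rising) or ET". For laboratory tests: "On subsequent days, blood and urine samples will be taken upon rising in the morning under fasted condition". For vital signs, 9.1.6 says: "Vital signs should be collected daily, predose and upon morning rising on days during confinement". I read the Day 2 sets as preceding that day's donepezil dose. The scheduled sets after donepezil are then:
- ECG: Days 3, 4 and 5; 3 of 3 lost.
- Vital signs: Days 3, 4 and 5; 3 of 3 lost.
- Laboratory: Days 3, 4, 5 and 8; 4 of 4 lost.

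One best-effort Early Termination set stands in their place. EEG timing is redacted and is not counted.

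**TAK-071 AUC∞.** Assume mono-exponential decline, so the share not yet observed at time t is exp(−t·ln2/t½). For t½ take 65 h and 140 h. These are the protocol's thresholds for changing the dosing duration (6.2.2.2), not observed values.

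| | t½ = 65 h | t½ = 140 h |
|---|---|---|
| Unobserved at 28 h | 0.742 | 0.871 |
| Unobserved at 168 h (full profile) | 0.167 | 0.435 |
| Extra share due to withdrawal | 0.575 | 0.435 |
| Decline seen, 4 to 28 h, in half-lives (24/t½) | 0.37 | 0.17 |
| Decline seen, 4 to 168 h, in half-lives (164/t½) | 2.5 | 1.2 |

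Differences are taken before rounding. With 74% to 87% of the area extrapolated from less than half a half-life of decline, AUC∞ is not usable. The full profile is itself imperfect at 17% to 44%.

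**What is kept.** By 28 h the 24 h sample has been drawn, and TAK-071 is at or near its maximum about 4 h after dosing (6.2.2.4). Three of the four primary TAK-071 parameters (tmax, Cmax, AUC24) are therefore available.

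**Other subjects.** For a donepezil-alone subject (1 of 3 per cohort) only the donepezil and safety losses apply, because TAK-071 samples from placebo subjects are mostly not assayed (9.1.15.1). In Cohort 16 the effect is smaller: Period 2 drug would stop under either wording.

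**The case against.** The strongest reply is that withdrawal keeps reports made with known allocation out of very small groups whose purpose is blinded tolerability, and that the primary endpoints survive anyway. Much of the second half stands.

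A reader might infer that the primary safety endpoints are lost for this subject. The documents do not support that:
- The event behind the blind break already counts toward the TEAE percentage.
- The markedly-abnormal-value endpoint needs only one qualifying postdose result. SAP 7.12.2 to 7.12.4 count unscheduled as well as scheduled measurements, so Day 1 results, tests done while treating the event and the Early Termination set all contribute.
- The request in 8.5 to assess before unblinding may yield a post-donepezil set.

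What is lost is the scheduled time course.

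Both documents allow AUClast when AUC∞ cannot be estimated in enough subjects. That helps less: this subject's AUClast would end near 28 h, against up to 168 h for the others.

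The bias argument is weak for ECG intervals, laboratory values and concentrations, which are largely objective. The SAP plans no statistical tests on the laboratory or vital sign summaries. The argument keeps some force for symptoms and later causality judgements, and flagging addresses that.

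The protocol already separates the two actions elsewhere. Section 7.5 distinguishes leaving the study from leaving study drug, and 13.3 describes a subject who stays in for all other assessments after a failed critical procedure.

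**Conclusion.** The point holds as a cheap improvement of low priority. After the last dose, the withdrawal clause in 8.5 removes scheduled observation without sparing the subject any drug. In the scenario the cost is half of the TAK-071 postdose samples, 10 of 14 donepezil samples, every scheduled post-donepezil ECG, vital sign and laboratory set, and a usable AUC∞, in 1 of 6 combination subjects. The effect on the primary safety percentages is partial.

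This rests on the chosen break time, on Day 2 assessments preceding donepezil, and on half-lives of 65 to 140 h with mono-exponential decline. The trigger is likely rare. The forward effect is mainly on Cohort 22 and any added single-dose cohorts.

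Two further inferences should not be drawn:
- That the subject could not be replaced. Replacement is discretionary and limited to withdrawals not for safety, but unblinding is not a named reason in 7.5. The withdrawal could be recorded as Other and replacement allowed. The text leaves this open.
- That 8.5 and 9.1.11 are in serious conflict. Section 9.1.11 directs a blind break at the subject's choice after a pregnancy, a ground 8.5 does not list, and 8.5 would then withdraw a male subject with a pregnant partner. But 9.1.11 can be read as a specific exception, and women of childbearing potential are excluded. It is a cross-reference to tidy.

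**What to change.** In Protocol 8.5, replace the withdrawal half of the sentence with: 'no further study drug is given; with the subject's agreement, the subject continues all remaining scheduled safety and PK assessments and the follow-up call (Cohort 16: the rest of the current period and the follow-up call), and data after unblinding are flagged.' The subject stays in the Safety and PK sets as the SAP defines them, with the flag shown in the listings.

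As a minor consistency edit, have 8.5 refer to the 9.1.11 pregnancy request as a permitted blind break.

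The cost is one sentence and one cross-reference, with no visits or samples beyond the existing schedule. The downside is that later subjective assessments and AE causality in flagged subjects are made unblinded.

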8.5.1 Sponsor PD Unblinding

A Takeda representative outside the main study team will receive the randomization schedule to analyze the PD data for interim analysis. This team member will not be involved in the conduct of the study or interpretation of any safety or PK data.

8.5.2 Sponsor Interim Analysis Unblinding

The main Takeda study team will be unblinded to Cohorts 1 to 15 and 17 to 22 data during the interim analysis and Cohort 16 will remain blinded.

8.6 Accountability and Destruction of Sponsor-Supplied Drugs

Drug supplies will be counted and reconciled at the site before being returned to the sponsor or designee or before being destroyed at the site following local site procedures with sponsor approval.

The investigator or designee must ensure that the sponsor-supplied drug is used in accordance with the protocol and is dispensed only to subjects enrolled in the study. To document appropriate use of sponsor-supplied drug (TAK-071 drug substance, DIC, and donepezil), the investigator or designee must maintain records of all sponsor-supplied drug delivery to the site, site inventory, dispensation and use by each subject, and return to the sponsor or designee, or destruction at the site following local procedures with sponsor approval.

Upon receipt of sponsor-supplied drug, the investigator or designee must verify the contents of the shipments against the packing list. The verifier should ensure that the quantity is correct and that

the medication is in good condition. If the quantity and conditions are acceptable, the investigator or designee should acknowledge the receipt of the shipment by signing the bottom half of the packing list and faxing per instructions provided on the form. If there are any discrepancies between the packing list and the actual product received, Takeda must be contacted to resolve the issue. The packing list should be filed in the investigator's essential document file.

The investigator or designee must maintain 100% accountability for all sponsor-supplied drugs (TAK-071 drug substance, DIC, and donepezil) received and dispensed during his or her entire participation in the study. Proper drug accountability includes, but is not limited to, the following:

- Continuously monitoring expiration dates if expiry date is provided to the investigator or designee.
- Frequently verifying that actual inventory matches documented inventory.
- Verifying that the log is completed for the drug lot used to prepare each dose.
- Verifying that all containers used are documented accurately on the log.
- Verifying that required fields are completed accurately and legibly.
- A site representative, otherwise uninvolved with study conduct, will review the randomization schedule and subject dosing log prior to Day 1 dosing and following dosing to ensure all subjects received the correct dose of study drug.

If any dispensing errors or discrepancies are discovered, the sponsor must be notified immediately.

The investigator or designee must record the current inventory of all sponsor-supplied drugs (TAK-071 drug substance, DIC, and donepezil) on a sponsor-approved drug accountability log. The following information will be recorded at a minimum: protocol number and title, name of investigator, site identifier and number, description of sponsor-supplied drugs, expiry date, and amount dispensed (including initials, seal, or signature of the person dispensing the drug). The log should include all required information as a separate entry for each subject to whom sponsor-supplied drug is dispensed.

All study drug not returned to the site by a subject must be investigated by the site and appropriately documented on the drug accountability log.

Prior to site closure or at appropriate intervals, a representative from the sponsor or its designee will perform sponsor-supplied drug accountability and reconciliation before sponsor-supplied drugs are returned to the sponsor or its designee for destruction. The investigator or designee will retain a copy of the documentation regarding sponsor-supplied drug accountability, return, and/or destruction, and originals will be sent to the sponsor or designee.

The investigator will be notified of any expiry date or retest date extension of sponsor-supplied drug during the study conduct. On expiry date notification from the sponsor or designee, the site must complete all instructions outlined in the notification, including segregation of expired sponsor-supplied drug for return to the sponsor or its designee for destruction.

